## **Qualitative Protocol Development Tool**

The research protocol forms an essential part of a research project. It is a full description of the research study and will act as a 'manual' for members of the research team to ensure adherence to the methods outlined. As the study gets underway, it can then be used to monitor the study's progress and evaluate its outcomes.

Please indicate the compatibility of this template with any existing templates you already use by stating one of the following on the front of each submitted protocol:

This protocol has regard for the HRA guidance and order of content

i

### STUDY SUMMARY

Study Title	A Feasibility study: The efficacy and safety of heat applied to the eyelids in enhancing the delivery of ocular hypotensive eye drops in the treatment of Primary Open Angle Glaucoma
Internal ref. no. (or short title)	Heat Application to the eye Lids to enhance Ocular drug delivery
Study Design	Interventional
Study Participants	Primary Open Angle Glaucoma/Ocular Hypertensive patients
Planned Size of Sample (if applicable)	24
Follow up duration (if applicable)	N/A

vi

Planned Study Period	12 months
Research Question/Aim(s)	To investigate whether applying heat to the eye lids of patients with POAG or OHT in combination with ocular hypotensive eye drops results in further lowering of IOP. Primary objective The primary objective of the study is to demonstrate that heat applied to the eyelids in combination with the instillation of anti-Glaucoma eye drops induces a further lowering of IOPs when compared to the use of anti- Glaucoma eye drops alone. Secondary objective The secondary objective of the study is to determine whether there is a timepoint during the course of the day (phasing) that demonstrates the largest difference in IOP following heat and hypotensive eye drop combination.

## FUNDING AND SUPPORT IN KIND

FUNDER(S) (Names and contact details of ALL organisations providing funding and/or support in kind for this study)	FINANCIAL AND NON FINANCIALSUPPORT GIVEN
North West Anglia NHS Foundation Trust	Sight Research UK

## **PROTOCOL CONTRIBUTORS**

[name] (Ophthalmologist), [name] (Optometrist), [name] (CTA/Ophthalmic technician) will be responsible for identifying suitable patients for the study. [name] or [name] will receive informed consent from the patients. [name] will be responsible for collecting data, writing the manuscripts and associated patient documents. Data analysis will be conducted by ARU or Imperial College statisticians (TBC). Dissemination of the results from the study will be completed by [name], [name] and [name].

The funder will not control the final decision regarding aspects of the study.

The protocol has been designed around similar previous studies and has involved the input of patients, members of the public or service users.

**KEY WORDS:** Heat, Hypotensive, Drug, Delivery, POAG, OHT, Ocular

#### **STUDY FLOW CHART**

Suitable patients identified and consented from Glaucoma clinics at HH and PCH-visual fields test completed One week prior to the first phasing visit the patient will be asked to start completing their drop compliance diary, continued for the duration of the study IOP phasing for POAG/OHT patients on topical therapy WITHOUT heat (no mask) - first visit IOP phasing for POAG/OHT patients on topical therapy WITH heat - second visit IOP phasing for POAG/OHT patients on topical therapy WITHOUT heat (wearing mask) third visit One to two weeks after completing the study a further visual fields test will be completed safety visit including a visual fields test and visual acuity measure Patient continues with their normal Glaucoma care

# Abbreviations

BCVA	Best corrected visual acuity
CI	Chief Investigator
CRF	Case report form
GCP	Good clinical practice
HH	Hinchingbrooke Hospital
IOP	intraocular pressures
MGD	Meibomian Gland Dysfunction
mmHg	millimeters of mercury
NWAFT	North West Anglia NHS Foundation Trust
OHT	Ocular Hypertension
ORA	Ocular Response Analyser
OSDI	Ocular surface disease index
P value	Probability value
PCH	Peterborough City Hospital
PIS	Patient information sheet
PGA	Prostaglandin analogue
PI	Principle investigator
PPI	Patient and public involvement
POAG	Primary Open Angle Glaucoma
QoL	Quality of life
SD	Standard deviation
VF	Visual fields test

### STUDY PROTOCOL

Title: A Feasibility study: The efficacy and safety of heat applied to the eyelids in enhancing the delivery of ocular hypotensive eye drops in the treatment of Primary Open Angle Glaucoma

## 1 BACKGROUND

## 1.1 Primary Open Angle Glaucoma and Ocular Hypertension

Glaucoma is a disease characterised by damage to the optic nerve (Weinreb and Khaw, 2004) and is the leading cause of reversible blindness (Blomdahl et al., 1997). Primary Open Angle Glaucoma (POAG) is the most common sub-type of the condition (Quigley and Broman, 2006) in which people typically present with open drainage pathways and intra ocular pressures (IOPs) that increase gradually. In Ocular Hypertension excessively high IOPs can occur in the absence of any other optic nerve involvement in the early stages (Gordon et al., 2002; Kass et al., 2002). Both these conditions require long term management via a variety of therapies currently available. The most common approach to treatment in Glaucoma care is still the use of topical hypotensive eye drops to reduce the IOPs-the only modifiable risk factor for the disease (Bateman et al., 2002). If effective treatment is not delivered for an individual, raised IOPs present a risk of optic nerve damage resulting in a progressive and permanent loss of field of vision (Quigley, 1999; Weber and Harman, 2005). In the UK it was estimated that in 2000 the prevalence of Glaucoma was 3.3% of the population over the age of 40 years and 5% of the population over the age of 80 years (Gray, et al., 2000). It has recently been reported that 20% of the eye clinic workload consists of Glaucoma patients (Fu, et al., 2023).

## 1.2 Route of administration for anti-hypotensive ocular drugs

Currently there are a number of hypotensive eye drops that are considered the first line of treatment in the medical management of POAG and OHT (Alexander et al., 2002; McKee et al., 2005). The topical application of these drugs is advised for use directly to the ocular surface followed by eye closure and punctal occlusion for up to two minutes (Huang and Lee, 1989). By following this procedure, it is hoped that the active ingredients in these eye drops stay in contact with the ocular surface (cornea) for the maximum amount of time before being expelled from the eye by lacrimation, tear dilution and tear turnover (Patton and Francoeur, 1978). It is estimated that <10% of the applied dose actually reaches the intra-ocular tissue that it is intended to act upon (Burstein and Anderson, 1985), since some of the drops will be flushed from the eye after stimulating reflex tearing (Gaudana et al., 2010) and the tightness of the corneal barrier at a cellular level prevents absorption (Bachman and Wilson, 1985). It has been recognised that there may be an alternative drug delivery route for certain molecules that is non-corneal. This route may be able to deliver adequate levels of the active

ingredient from the instilled drop to the iris-ciliary body complex rather than the traditional aqueous humour levels pathway (Ahmed and Patton, 1985).

## 1.3 Previous strategies to enhance drug delivery

Several strategies have been employed in an attempt to enhance the penetrative properties of topical eye drops including combining the Glaucoma drug with a preservative (Sasaki et al., 1995) or EDTA (Grass et al., 1985; Sasaki et al., 1995). These additives were thought to weaken the tight junctions of the corneal epithelium to aid in the drop reaching its designated target. Unfortunately, these agents have had limited success and an often-detrimental effect to the ocular surface (Grass et al., 1985; Noecker, 2001) and as such resulted in reduced adherence to the eye drop regime by the patients (Friedman 2009; Sleath 2006).

## 1.4 Applied heat to enhance drug delivery

There has been some anecdotal evidence that the application of heat to the evelids after instillation of topical mydriatic drops promoted drug permeation and aided in the breakdown of posterior synechiae in acute uveitis cases (Hobbs, 2013). It is on this theory that this proposed feasibility study is based: to find out whether application of heat to the eyelids in combination with the instillation of ocular hypotensive eye drops could lower the intraocular pressure further. This theory has not been studied in any detail and is a new approach for hypotensive therapy in POAG and OHT. The mechanisms in which the application of heat may affect the efficacy of ocular eye drops are still a subject of speculation. However, there have been a number of studies in recent years that have put forward some potential theories linked to blood flow and ocular surface temperatures. Li et al (2018) proposed that blood vessel ischaemia in Glaucoma was a contributing factor to the disease pathway and using a novel temperature-measuring device on rabbits concluded that the retrobulbar blood flow was increased significantly following heat application to the ocular surface. They stated that since Glaucoma sufferers have a lower-than-normal blood supply (Garhofer et al., 2010) the approach of heating the eyelids could provide a convenient and non-invasive technique with no systemic side effects in which to aid the treatment of Glaucoma (Li et al., 2018). The ocular surface temperature in general has been recorded as lower when compared to healthy subjects. Garcia-Porta et al (2019) demonstrated cooler central corneal temperatures and on eye opening (following a period of eye closure) a significant cooling of the ocular surface in glaucoma sufferers compared to the control. The group concluded that both ocular blood supply and tear film stability are important factors in the make-up of Glaucoma disease. Ambient temperatures have also been documented to influence the IOP of glaucoma patients. A significant reduction in IOP was measured in Glaucoma patients during the summer (13.9 ± 11.1°C) compared to the winter  $(3.28 \pm 4.8$ °C). The group purported that this effect was due to the cooling of the aqueous humour which in turn reduced its fluidity and circulation. contributing to the increased IOP measure (Krebs et al., 2019). It is clear that temperature does have an influence on the IOPs and ocular surface in general in Glaucoma patients and warrants further investigation.

### 1.5 Effect of heat on the cornea

There is a possibility that the application of heat to the eye could affect corneal hysteresis. This is defined as the difference in pressure when the cornea bends inwards and then outwards during and following air non-contact applanation. The difference in millimeters of mercury (mmHg) can be used to gauge the elasticity of the cornea, specifically its ability to absorb pressure. Corneal thickness and hysteresis are both important factors in the management of Glaucoma and the former has been revealed to be a strong independent risk factor for Glaucoma progression following the results of the Ocular Hypertension study (Gordon et al., 2002). Several studies have also confirmed that low corneal hysteresis also correlates with an increased risk of Glaucoma progression as evidenced by visual fields outcomes (Congdon et al., 2006; DeMoraes et al., 2012). Lower corneal hysteresis has also been shown to be associated with optic nerve damage (Vu et al., 2013). Unlike corneal thickness, hysteresis is often different between the two eyes and can vary with IOP changes and responses to anti-hypotensive medications are likely to be more significant with lower corneal hysteresis (Agarwal et al., 2012). It is likely that corneal hysteresis could also explain the often-asymmetric presentation of Glaucoma with damage often being worse in the eye that has lower hysteresis (Radcliffe, 2014). To detect any changes to corneal hysteresis by the application of heat during this study the IOPs will be measured using the Ocular Response Analyser (ORA) tonometer which will give the average value of hysteresis after three measures in each eye.

## 1.6 Reducing the burden on patients and NHS finances

Currently the annual mean cost per patient for Glaucoma treatment in the UK is £475 (Rahman et al., 2013) with increasing costs being incurred if an individual progresses on to require Glaucoma surgery (Traverso et al., 2005). If the efficacy of the drops currently being used by patients could be enhanced with the addition of heat to the eye lids, it may reduce the need for increasing a patient's treatment to dual therapy drops reducing the lifelong burden of extra drop instillation on the patient (Nordstrom et al., 2005) and even improving compliance. In addition, it could eliminate the potential need for progressing to surgery, which would lessen the risk of a secondary infection (Ang et al., 2010) due to the invasive nature of the procedures and in both cases would reduce the overall financial burden for the NHS (Fiscella et al., 2009; Tham et al., 2014; Varma et al., 2011).

Along with the day-to-day costs to the NHS of Glaucoma treatment (topical and surgical) the condition also puts sufferers at an increased risk of falls due to their compromised field of vision. A recent study by McGinley et al (2020) estimated that the cost of admissions for falls where the patients also had a diagnosis of glaucoma was £28.6 million annually in the UK. This was extrapolated from data collected at Maidstone and Tunbridge Wells NHS trust where 11.7% of admissions for falls in a calendar year involved the aforementioned patient group (McGinley, et al., 2020).

Glaucoma is a chronic condition that once diagnosed will generally require some form of treatment for the remaining lifetime of the patient. Rahman et al (2013) conducted a study to calculate the average annual mean cost based on patients at the Glasgow Royal Infirmary. The yearly cost of non-drug and drug therapies for each patient averaged at £475 (Rahman, et al., 2013). In a more recent study analysing the costs of Glaucoma clinics in the UK Fu, et al., reported that the annual cost of a Glaucoma patient to the NHS between 2013-2018 ranges from £352-£512 depending on disease severity (Fu, et al., 2023). The annual cost of Glaucoma medication in England in 2018 was 114.2 million and represented the costliest indication within ophthalmic prescriptions (Hogg and Connor, 2020).

This disease contributes to a significant proportion of the NHS expenditure annually with one study reporting that the UK spent £300 million on Glaucoma care in 2002, with a noticeable increase in the new cases of glaucoma receiving treatment these costs are likely to escalate further (Rouland et al., 2005).

The economic burden in terms of additional treatments that are required and hospital visits, to the personal burden of living with the condition of glaucoma will increase as the disease progresses and the glaucomatous damage worsens and in general has an impact on the quality of life for the patient even in the early stages.

As the glaucomatous damage worsens for the patient, the burdens in terms of economics and the need for additional treatments and close monitoring via hospital visits to personal in terms of quality of life will continue to impose increasing costs on the NHS costs and resources. This cost increases incrementally by approximately £58 for each stage that the disease becomes more severe, and this does not take into account the vision rehabilitation and low vision service costs (Traverso et al., 2005).

## 2 RATIONALE

To investigate whether applying heat to the eyelids in combination with ocular hypotensive eye drop instillation, can enhance the efficacy of ocular glaucoma medication and lead to a further lowering of IOP. Although there is anecdotal evidence that ocular drug can be enhanced with the application of heat in combination with mydriatics in acute uveitis patients, this theory has not been studied in any detail and is a new approach for hypotensive therapy in POAG and OHT. The prediction is that applying heat to the eyelids will increase the efficacy of instilled drops and result in a further lowering of IOP in individuals diagnosed with POAG/OHT. In this study we aim to use commercially available goggles used to heat the eyelids up to a temperature of 42.5°C for a period of ten minutes. This approach has been recommended by the DEWS II for the treatment of meibomian gland dysfunction (MGD) and when combined with lid massage aids in the unblocking of the Meibomian glands (Jones et al., 2017). Several studies have shown the safety and efficacy of these devices (Pult et al., 2012; Castillo et al., 2014; Villani et al., 2015). Pending the results of this feasibility study, we would aim to provide proof of concept that the addition of heat to the eyelids enhances the

efficacy of anti-hypotensive eye drops with a view to using this as a basis for a larger scale study in the same field. From this approach we hope to start providing information and scientific basis for the use of existing therapies in this new patient group to help enhance the treatment for this chronic sight threatening disease.

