## **3 THEORETICAL FRAMEWORK**

There is a lack of evidence that applying heat to the eyelids may improve ocular drug delivery in all areas of Ophthalmology. This feasibility study has chosen to focus on the hypothesis that the addition of heat will enhance the efficacy of ocular hypotensive eye drops used in the treatment of POAG and OHT will result in a significant reduction in IOPs when compared to the use of ocular hypotensive eye drops alone. There is a great potential use for a favourable outcome from this study in that it could reduce the need for additional eye drops or progression to surgery. It is currently well accepted that applying heat to the eyelids is a safe procedure and is a mainstay of treatment for MGD and it is this approach that will be used in this study to determine whether ocular drug delivery can be enhanced. The clinic at Hinchingbrooke (HH) and Peterborough City Hospital (PCH) runs regular Glaucoma clinics with a large number of these patients who have an active diagnosis of POAG or OHT. Patients will be approached that currently use their eye drops in the morning as it is thought that this in combination with the heat will enhance the effect further. If proof of concept is realised through this feasibility study, then a larger scale project will be put forward to investigate whether the effect is demonstrated in all Glaucoma hypotensive eye drops and whether it is also effective if patients instil their drops in the evening. It is acknowledged that the effectiveness of the glaucoma eyedrops could be increased with heat alone and/or with the additional beneficial effects imparted on the ocular surface by virtue of improving any underlying MGD condition. As such the baseline MGD status of all patients will be recorded to determine to what level the improvement of this condition may affect the overall outcome.

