### 4.2 Outcome

Should this study confirm the proposed hypothesis it would be the intention of the researchers to expand the scope of the study by collaborating with other NHS trusts to increase subject recruits, include broader patient demographics and a wider range of anti-hypotensive eye drops to investigate whether a particular class of drug would be more sensitive to temperature and whether gender or race has an effect on the IOP. Although it is not within the scope of the current budget applied for, future studies would also include a non-glaucomatous control group who would undergo the same IOP phasing protocol with and without the heated goggles to establish whether heat alone would be sufficient to reduce the IOP in comparison to the combination of heat and anti-hypotensive eye drops in Glaucoma patients. It would be the intention of this research team to apply for further funding to support this action from charities such as Glaucoma UK which encourage applications from Optometrists to the open call Glaucoma care grant.

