The patient will attend the clinic for three separate visits each approximately one week apart. starting with phasing 'without heat', then phasing 'with heat' and lastly phasing wearing the Blephasteam mask but with no heat as a control. The Blephasteam mask will only be used on the days of the clinic visits, the participants will not be required to use the device at home. The water carrier inserts for the masks will be designated to the same patient throughout the study for hygiene reasons. The inserts for the mask will be moistened and fitted according to the manufacturers' instructions. The wireless device will be left to reach temperature for 3-4 minutes then the patient will be asked to wear the mask and be instructed to keep their eyes closed, this occurs once at the start of each visit. The device warms the ocular surface for a set time of 10 minutes, after which the participants will remove the mask and instil their habitual Glaucoma eyedrops. They will be instructed to close their eyes and apply light pressure on the inner corner of the eye for 30 seconds. The IOP will then be measured at the first time point with the ORA and Goldman devices. Although both eyes will be treated with the heat mask only the right eve results (to eliminate bias) will be used for the statistical analysis. During the visits the patients' will have their best corrected visual acuity (BCVA) reviewed before and after measurements are taken. IOPs are measured first using the ORA tonometer (Reichert Inc., Germany) followed by the Goldman tonometer (Haag-Streit AG, Switzerland) five minutes later as per previous studies measuring IOP with the sequential use of tonometers (Tejwani et al., 2015). These IOP measures are taken at five set time points during the day called 'phasing': 08:30 +/- 30 mins, 10:30 +/- 30 mins, 12:30 +/- 30 mins, 14:30 +/- 30 mins and 16:30 +/- 30 mins. An average of three measures will be taken using the ORA machine, when using the Goldman tonometer three measures will only be taken if the first two are not within >2mmHg of each other. The procedure for the Goldman tonometer will be as follows: Two individuals (an operator and a reader) will perform the readings for the study visits. The operator will be responsible for operating the slit lamp, tonometer, and the instrument dial, while the reader will read and record the results. A full anterior segment slitlamp examination will be performed at the end of each phasing visit to ensure there are no adverse effects experienced following the treatment, including grading of the Meibomian glands (Efron scale). Additional assessments include adverse events and quality of life and ocular questionnaires.

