#### 11. APPENDICIES

## 11.1 Appendix 2 – Schedule of Procedures

Procedures	Visits					
	Identification and consent	Visit 1- phasing without heat	Visit 2- phasing with heat	Visit 3-phasing with mask but no heat	Visit 4 – safety check	
Informed consent	x					
Demographics	x					
Medical and ocular history	х					
QoL questionnaires		x	x	X		
OSDI questionnaire		x	x	x		
Visual fields	x				x	
Drop compliance diary	x	x	x	X		
Slit-lamp examination		x	x	X		
Corneal fluorescein stain (Oxford grading)		x	x	х		
Meibomian gland dysfunction (Efron grading)		x	x	x		

HALO – PROTOCOL

			Nort	<del>h West Anglia</del>		1
Conjunctival hyperaemia (Efron grading)		х	x	HS Foundation Trust		
Application of Blephasteam®			x			
Instillation of habitual hypotensive eye drops		Х	x	x		
IOP @ 08:30 +/- 30 mins		х	x	x		
IOP @ 10:30 +/- 30 mins		х	x	x		
IOP @ 12:30 +/- 30 mins		х	x	x		
IOP @ 14:30 +/- 30 mins		х	x	x		
IOP @ 16:30 +/- 30 mins		х	x	x		
Adverse events		Х	x	х		
Far best corrected visual acuity (BCVA)		х	x	x	х	
Verification of inclusion and exclusion status	x					

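### The drop is given at every visit where IOP is measured, so a further fall with heat cannot be read as enhanced drop delivery or efficacy, which is how the title and Sections 2, 2.1 and 3 frame it

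*Protocol*

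**What the plan says.** **The claim.** The full title and the short title both present lid heat as a means of enhancing drug delivery. Section 2 predicts that "applying heat to the eyelids will increase the efficacy of instilled drops and result in a further lowering of IOP". It then says that, depending on the results, "we would aim to provide proof of concept that the addition of heat to the eyelids enhances the" efficacy of the drops. Section 2.1 describes repurposing the goggles to see whether they strengthen the effect of the drops. Section 3 gives the hypothesis as "the addition of heat will enhance the efficacy of ocular hypotensive eye drops", leading to a significant IOP reduction compared with drops alone.

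**The objective.** The primary objective in Section 4 is narrower: a further lowering of IOP with heat plus drops than with drops alone.

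**The design.** Section 5 has three phasing visits, "starting with phasing 'without heat', then phasing 'with heat' and lastly phasing wearing the Blephasteam mask but with no heat as a control". At the mask visits the device is worn first, "after which the participants will remove the mask and instil their habitual Glaucoma eyedrops". In Appendix 2 the row "Instillation of habitual hypotensive eye drops" is marked at Visits 1, 2 and 3, the only visits with scheduled IOP measurements.

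**The acknowledged gap.** Section 4.2 puts a non-glaucomatous control group outside the present budget. Its purpose in future studies would be "to establish whether heat alone would be sufficient to reduce the IOP in comparison to the combination of heat and anti-hypotensive eye drops".

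**The concern.** To say that heat enhances a drop's delivery or efficacy is to say that the drug does more when heat is present. To say that heat plus drop lowers IOP more than drop alone is weaker: it would also be true if heat lowered IOP by itself and left the drug's action unchanged. The protocol tests the second statement and words its conclusion as the first.

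The rival explanation comes from the protocol. Section 1.4 cites an association between ambient temperature and IOP in glaucoma patients, explained through aqueous fluidity, which needs no drug. It concludes: "It is clear that temperature does have an influence on the IOPs and ocular surface in general in Glaucoma patients". The unheated-mask visit controls for wearing the mask, not for heat acting independently of the drug.

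At stake is what a positive result may be said to show. As worded, a purely direct effect of heat would be reported as proof of concept for drop enhancement.

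**Working it through.** The protocol gives no figure to reproduce here. The check is whether the two effects are separately estimable from the conditions compared.

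**Model.** Let *d*, *h* and *m* be 1 when the drop, heat and mask are present and 0 otherwise. Then

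mean IOP = μ + D·d + H·h + M·m + E·(d × h)

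H is the direct effect of heat and E is the extra effect of the drop when heat is present, that is, enhancement. Period effects are left out, which favours the protocol because the visit order is fixed.

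**Conditions** (Section 5 and Appendix 2):

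| Visit | d | h | m | Expected IOP |
|---|---|---|---|---|
| 1, no mask | 1 | 0 | 0 | μ + D |
| 2, heated mask | 1 | 1 | 1 | μ + D + H + M + E |
| 3, unheated mask | 1 | 0 | 1 | μ + D + M |

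**What can be estimated.**

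- Visit 3 − Visit 1 = M
- Visit 2 − Visit 3 = H + E
- Visit 2 − Visit 1 = H + E + M

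Because d = 1 in every row, the columns for H and E are identical. The design matrix has rank 3 for five parameters. H + E and M are estimable; H alone and E alone are not.

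**Illustration.** Assume μ = 22 mmHg, D = −5 and M = 0; the protocol gives none of these values. Set H + E = −1.5, the difference that Section 5.2.2 treats as significant.

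| Split | H | E | Visit 1 | Visit 2 | Visit 3 |
|---|---|---|---|---|---|
| All direct heat | −1.5 | 0 | 22 − 5 = 17.0 | 17.0 − 1.5 = 15.5 | 17.0 |
| All enhancement | 0 | −1.5 | 17.0 | 15.5 | 17.0 |
| Even mix | −0.75 | −0.75 | 17.0 | 15.5 | 17.0 |
| Opposing effects | −2.0 | +0.5 | 17.0 | 15.5 | 17.0 |

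The three visits look the same in every row. In the last row the direct effect exceeds the whole difference (2.0/1.5 = 133%).

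**What separation would need.** Adding only a heated condition without the drop (μ + H + M) leaves four equations for five unknowns, and H and E stay inseparable. An unheated condition without the drop (μ + M) is needed as well: the difference between the two no-drop conditions gives H, and E = (Visit 2 − Visit 3) − H. This states what identification requires; it is not a proposal to withhold treatment.

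**The case against.** The strongest reply is that the trial does not need the separation. The primary objective in Section 4, the aim and the summary in Section 7.4 ask only whether IOP differs with heat added, and the conditions compared match that question. This stands in full. A reader might infer that the missing conditions undermine the primary comparison; on this ground they do not.

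The second reply is that the limit is largely disclosed. Section 4.2 defers heat alone to future studies, Section 1.4 calls the mechanism speculative, and Section 3 concedes an ocular-surface route and records baseline meibomian gland status. This stands in part. The disclosures are not carried into the conclusion in Sections 2 and 3. The control planned in Section 4.2 is a different, non-glaucomatous population, and baseline gland status does not measure a direct effect of heat on IOP.

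The third reply is that the wording is tentative. Section 2 only aims at proof of concept, Section 3 is conditional, and enhanced efficacy could loosely mean a better result from treatment with heat added. The tentativeness is real: a reader might infer that the plan promises proof, and it does not. But being tentative about the result does not change what a positive result would be called, and the title's reference to delivery does not admit the loose reading.

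The rabbit blood-flow study in Section 1.4 should not be counted as evidence of a direct IOP effect. It appears there among theories of how heat might help drops, and no IOP lowering is reported from it. Only the ambient-temperature study links temperature to IOP without drops.

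**Conclusion.** The point holds as one about the stated conclusion. The trial can estimate the total effect of adding lid heat to a prostaglandin drop. It cannot attribute any part of that effect to enhanced delivery or efficacy, yet the title and Sections 2, 2.1 and 3 would do so. This rests only on the drop being given at all three IOP visits, which Section 5 and Appendix 2 establish, and is independent of sample size, variance and test.

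No numerical size can be put on the misattribution. A reader might infer that the direct share lies somewhere between 0 and 100% of the observed difference. That is not a valid bound: opposing effects take it above 100%, and the fixed visit order could contribute to the difference with no heat effect at all.

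Nor do the documents show that the follow-on programme would be misdirected. Section 4.2 plans both the drug-class question and a heat-alone comparison, so there is no ground here for making one conditional on the other.

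**What to change.** - **Title, short title, and Sections 2, 2.1 and 3:** bring these into line with the primary objective in Section 4. The hypothesis and permitted conclusion could read: *lid heat added to established PGA monotherapy lowers IOP further than PGA without heat.*
- **Add one sentence:** *a positive result will not be reported as enhanced drug delivery or drop efficacy, because no visit measures IOP without the drop, with and without heat.* The reason should name both missing conditions, since heat without the drop would not be enough by itself.
- **Cross-refer to Section 4.2**, so that the limitation stands beside the claim it limits.

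The cost is wording and a narrower claim. No visit, measurement, treatment, sample size or test changes. The title and text changes would go through the amendment route in Section 8.2.
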